### 3. Study termination

- if patient has no pain or greater than 50% reduction in pain scores as compared to the pretreatment pain score, then outpatient subjects will be monitored in the SPU for 1 hour. If no clinically significant side effects are present after one hour, then the IV will be removed and he will be discharged with appropriate instructions from primary headache provider for home care and follow-up. Discharge criteria will follow CMC Perianesthesia Department policy for discharge, Policy Number 1.06. Inpatient subjects who have no pain will resume standard care treatment and will be discharged at the discretion of the attending service.
- if patient has less than 50% reduction in pain scores, the study investigators will continue with DHE protocol according to standard of care.

### 4. Follow-up 24 and 48 hours after infusion via phone call to evaluate headache status and recover following information:

- i) pain score (via Numeric Pain Rating Scale) at that time
- ii) if not pain-free, when did the headache return
- iii) side-effects from infusion

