**1. Introduction and Purpose:**

Propofol has been used in adult populations to treat migraines as an abortive agent. We plan to investigate its efficacy as an abortive agent in the pediatric population when administered as a safe low-dose infusion. Goals of the study are to:

1. Evaluate efficacy of low-dose propofol infusion as an abortive agent in pediatric migraine headaches
2. Evaluate effective and safe dosing limits in pediatric populations
3. Evaluate duration of effect reached from a low-dose propofol infusion as an abortive agent

Endpoints for the study will be:

1. Number of enrolled patients
2. Safety endpoints reached, including: cardiopulmonary depression, excessive somnolence

Risks of the study are minimal due to the use of sub-anesthetic dosing of propofol under the guidance and supervision of a board certified pediatric anesthesiologist with the appropriate monitoring equipment and readily available emergency equipment. We hope to demonstrate more rapid improvement and decreased side-effect as compared to standard care.

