Dihydroergotamine is an ergot alkaloid. Following the vascular theory of migraine pathophysiology, DHE has vasoconstrictive properties and is marketed for migraine therapy. (11) Although available to be administered via multiple routes, intravenous (IV) DHE is used to abort migraines refractory to the above therapies. Its administration, at this time, requires admission to the hospital or infusion as an outpatient in a clinical setting. As an inpatient, our current protocol requires premedication with anti-emetics and DHE dosing every six hours for up to twenty doses of DHE on a titration schedule. This requires an admission of up to five days for DHE therapy. As an outpatient, the patient will only receive one dose of DHE, which may or may not be efficacious (data show a 60% reduction in headache severity at one hour with no discussion of total resolution). (11) DHE has significant side-effects including: nausea (32%), chest tightness and mild systemic burning (8%), leg cramps (7%), vomiting (6%), increased blood pressure (5%). (11)

5-Hydroxytryptamine receptor agonist “triptan” therapy, also available in multiple modalities, has demonstrated both efficacy and safety. (2) With oral, intranasal and subcutaneous routes available, many migraine sufferers have preparations available to them at home as a component of the migraine exacerbation plan formulated by their physician.

Propofol (Diprivan) is a short acting lipophilic intravenous general anesthetic. Propofol is currently classified as a sedative-hypnotic and is used as an anesthetic agent.

It is marketed as 10mg/ml emulsion. Its mechanism of action is unrelated to any currently used barbiturate, opioid, benzodiazepine, or imidazole. As an intravenous anesthetic agent it causes global central nervous system depression presumably through GABA receptors and possibly by decreasing glutamatergic activity via NMDA receptor blockade.

Propofol is distributed to all tissues in the body rapidly following intravenous administration. Anesthetic results are dose dependent. There is rapid equilibration of the blood and brain concentrations (1 -3 minutes). Propofol is highly protein-bound (>95%) and metabolism is via rapid glucuronide conjugation in the liver. Duration of action of a bolus injection is 3 -5 minutes. Reported side effects include hypotension, arrhythmias (bradycardia or tachycardia) and burning or pain at injection.

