If propofol infusion is not successful in resolving headache, then the subjects will proceed with DHE infusion per standard of care. If the subject still has no relief, the study investigators will discuss further options with the subject and parents, including hospital admission for further therapy for outpatient subjects.

For all subjects who receive propofol infusion, follow-up will occur at 24 and 48 hours via phone call to evaluate headache status and recover information on headache symptoms and side effects.

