## ETHICAL AND ADMINISTRATIVE SECTION

## **A. Potential patient benefit**

The study aims to show efficacy of a propofol infusion, performed in a controlled and monitored situation with patient safety paramount, will have improved efficacy in providing an abortive therapy for acute migraines in patients refractory to their home regimen. We also aim to show decreased side-effects and sustained headache improvement as compared to DHE infusion. If successful, propofol will be an improvement in treatment and prevent unnecessary emergency center visits and prolonged hospital admission for alternative therapies.

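### The 24 h and 48 h calls ask when the headache returned only if the child is in pain at the call, so relapses gone by both calls need not be recorded and statements about durability lean towards longer relief

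*Protocol*

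**What the plan says.** Protocol METHODS B, item 4, lists three things to recover at each call: "pain score (via Numeric Pain Rating Scale) at that time", then "if not pain-free, when did the headache return", then "side-effects from infusion".

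The Concise Summary says that for every child who receives propofol "follow-up will occur at 24 and 48 hours via phone call", in order to "evaluate headache status and recover information on headache symptoms and side effects". The SAP Study Overview repeats this in the past tense. Neither adds a question. The Data Collection list (Protocol section 8) has no field for headache or acute treatment between the infusion and a call.

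On durability, goal 3 of Protocol section 1 is to "Evaluate duration of effect reached from a low-dose propofol infusion as an abortive agent", and the Potential patient benefit section hopes to show "sustained headache improvement as compared to DHE infusion". The formal secondary outcome called duration of effect is narrower. In both documents it runs from the end of propofol to discharge criteria or, if treatment is ineffective, to the start of new therapy.

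The SAP (Statistical Analysis) uses the call data in two ways, both by paired t-test: mean score against baseline, and mean percent change from baseline. It gives no rule for recurrence or for treatment taken in between.

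**The concern.** Item ii follows a score taken at the moment of the call, so its condition is naturally read as pain status at that moment. A child at 0 is not asked about recurrence. The protocol itself makes the problem sequence plausible: under Study termination, outpatient responders go home with home-care instructions, and the Background says of triptans that "many migraine sufferers have preparations available to them at home". Relapse, home treatment and a low score at the call can then follow one another without trace.

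The same item also fails children who never became pain-free. They are asked when a headache that never left came back, so recorded times can mix recurrence with persistence.

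At stake is the only planned information on how long relief lasts after discharge. The primary result is not at stake.

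**Working it through.** The documents state no figure to reproduce here. The check is what item 4, followed as written, records for each possible course.

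| Course after infusion | Item ii asked? | Required record |
|---|---|---|
| A. Pain-free and stays so | No | Score 0 at both calls, no return: correct |
| B. Pain-free, headache returns (say at 6 h), resolves or is treated, 0 at both calls | No | Same as A |
| C. Pain-free, headache returns and is present at either call | Yes | Time of return |
| D. Responder with residual pain, say 9 to 4, still in pain at a call | Yes | A return time for a headache that never left |
| E. Non-responder, goes on to DHE, still in pain at a call | Yes | As D |
| F. Non-responder, goes on to DHE, 0 at both calls | No | Score 0, with no treatment noted at the call |

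Row D arises because response includes a reduction above 50%: (9 − 4)/9 = 55.6%.

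**Direction.** B cannot be told from A. No course turns a child who stayed pain-free into a recorded relapse. Among children who became pain-free the error therefore runs one way. It is confined to relapses absent at both calls; those in row C are captured.

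**Effect on the SAP analysis.** A child with baseline score B and 0 at 24 h contributes a change of B to the paired test. That is so whether relief was continuous (A), restored by home treatment (B) or obtained after DHE (F). The score is correct as pain at that time. What is lost is whether propofol alone accounts for it.

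**Scale, for illustration only.** Suppose someone used the calls to report the proportion of treated children with sustained relief to 48 h. The overstatement would be p × R × q, where:
- p = response rate, set at 80%, from the small retrospective pediatric review of bolus dosing in the Protocol Background;
- R = share of responders who relapse by 48 h, assumed 20% to 60%;
- q = share of those relapses absent at both calls, assumed 25% to 75%.

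With 38 participants (SAP, Sample Size Considerations):
- Low: 0.80 × 0.20 × 0.25 = 0.04, or 4 points; 38 × 0.04 = 1.5 children.
- Middle: 0.80 × 0.40 × 0.50 = 0.16, or 16 points; 38 × 0.16 = 6.1 children. True 0.80 × 0.60 = 48%; apparent 48% + 16% = 64%.
- High: 0.80 × 0.60 × 0.75 = 0.36, or 36 points; 38 × 0.36 = 13.7 children.

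R and q have no source in the documents, and the plan never computes this proportion. The width of the range shows only that the size is unknown.

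**The case against.** A reader might infer that missed relapses are counted as sustained relief, or that the duration-of-effect outcome is biased. The documents support neither. They define no sustained-relief endpoint, and duration of effect ends before the calls can bear on it. The primary outcome is not defined on the calls, and for the SAP's mean scores a child at 0 is rightly scored 0. All of this stands and limits the point to interpretation of the 24 h and 48 h data.

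Item 4 is a list of information to recover, not a verbatim script, and the Concise Summary speaks more loosely of headache status and symptoms. A careful caller may have asked more. That is fair, but nothing requires it, and item 4 is the specific instruction.

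The sentence about triptans at home concerns migraine sufferers in general. These children have had headache for more than 24 hours at a score of 6 or more, and the benefit section calls such patients refractory to their home regimen. Relapses cleared by home treatment may be few. This bears on the size, not on the direction.

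Missed relapses are not all beyond recovery. Inpatients' headaches and drugs may be charted, and repeat infusions may reveal some relapses, although the protocol plans no such review.

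Finally, the hoped-for comparison with DHE has no comparison arm, so better questions would not supply it. The SAP also describes follow-up as already done, so a new question cannot change those data.

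**Conclusion.** The point holds as a secondary data-collection gap. Followed as written, the calls require no record of a relapse that has gone by both calls, or of acute treatment in between. They also attach a return time to headaches that never cleared. Any claim from these calls about how long relief lasts is biased towards longer relief, by an amount the documents do not allow to be estimated.

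This rests on two readings: that the condition in item ii refers to pain at the call, and that callers kept to the list. If callers routinely asked about interim headache and treatment and wrote the answers down, the gap is smaller than the text implies.

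**What to change.** At each call, ask every child, whatever the current score:
- (a) whether they were ever pain-free after the infusion;
- (b) whether headache has returned or worsened since discharge or the last call, even if it is gone now, and when;
- (c) whether any acute headache medicine, emergency visit or new admission occurred, and when.

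Record preventive medicine separately, and likewise an inpatient's continuing admission and standard care, so that neither counts as relapse. A rule that treated any medicine or admission as failure would misclassify inpatient responders, who resume standard care by design. For children with residual pain record time to worsening instead of return; for non-responders record persistence.

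In the SAP, keep the planned comparisons and also report the 24 h and 48 h results by recurrence and by acute treatment received, including DHE.

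For children already followed, check call notes and charts for this information. Where it is absent, report the scores as pain at the time of the call, unadjusted for later treatment, state the direction of the bias, and do not describe them as sustained relief.

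The cost is a few lines on calls already planned, with no extra contact, plus a chart check for past participants. Recall over a day is imperfect, and the durability result may look less favourable.

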## C. Consent Process and Documentation

Patients will be prescreened when they schedule an appointment at CMC for DHE infusion, for treatment of migraine headaches; or upon consult to the pain service for inpatients. A member of the study team will contact the family by phone in advance of the visit, or in person when the family is available in the hospital. If the patients express interest in study participation, they will meet with the study investigator to establish eligibility and discuss the risks/benefits of the study. The investigator will emphasize the voluntary nature of participation. The study investigator or research personnel will review the consent form and HIPAA authorization with the patient and their legal guardian. If the family decides to participate, then informed consent will be obtained (and assent if applicable). Copies of the signed forms will be given to the patient, and the consent process will be documented in EPIC.

## ETHICAL AND ADMINISTRATIVE SECTION

## **A. Potential patient benefit**

The study aims to show efficacy of a propofol infusion, performed in a controlled and monitored situation with patient safety paramount, will have improved efficacy in providing an abortive therapy for acute migraines in patients refractory to their home regimen. We also aim to show decreased side-effects and sustained headache improvement as compared to DHE infusion. If successful, propofol will be an improvement in treatment and prevent unnecessary emergency center visits and prolonged hospital admission for alternative therapies.

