#### *Secondary outcomes:*

- Time to beginning of effect (from the beginning of the propofol infusion till first improvement in pain score noted)
- Duration of effect (from the end of propofol administration till discharge criteria are meet or if treatment is ineffective, till start of new therapy)
- Total propofol dose based on weight.

Goal of subjects to be consented include: 30 to demonstrate effect

Subjects may receive multiple treatments if propofol infusion is effective in reducing headache symptoms.

**Concise Summary:** We will be enrolling subjects who are scheduled to undergo DHE infusion for treatment of migraine headaches as part of standard medical care. Subjects will be identified from the investigators' patient list, of children presenting to the Headache Clinic in the Pain Management Clinic for treatment of migraine headache or who have been admitted to the hospital for treatment of migraine headache. Patients who will be treated at the SPU or during inpatient admission by the DHE protocol will be evaluated for eligibility prior to the visit. If the investigator determines that they would be

eligible, the family will be contacted in advance of the visit to discuss possible participation. An investigator will be present at the visit to discuss the study in further detail and answer any questions, and informed consent will be obtained prior to any study procedures are performed.

Prior to initiation of DHE infusion, the subjects will receive sub-anesthetic doses of propofol infusion: 20 mcg/kg/min for 10 minutes, followed by an increase to 30 mcg/kg/min for 10 minutes and then by an increase to 40 mcg/kg/min for 40 minutes. The propofol infusion will be terminated if:

- The patient has no pain, or greater than 50% reduction in pain scores as compared to the pretreatment pain score
- After completing 40 minutes of propofol infusion at 40 mcg/kg/min irrespective of the pain score
- If the anesthesiologist feels cardio-pulmonary depression, airway obstruction or over sedation (Ramsay Sedation Score greater than 3) has occurred

If the propofol infusion is effective in resolving headache symptoms, then subjects will be monitored for at least 30 minutes after termination of infusion. Outpatient subjects would then be discharged home; inpatient subjects would resume standard care treatment.

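### The protocol aims to improve on DHE without a comparator, and the SAP's 24- and 48-hour results do not set apart data collected after DHE

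*Protocol*

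**What the plan says.** **Comparative statements.** The protocol, under Potential patient benefit, says "We also aim to show decreased side-effects and sustained headache improvement as compared to DHE infusion". Its Introduction and Purpose adds "We hope to demonstrate more rapid improvement and decreased side-effect as compared to standard care".

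**Order of treatment.** The Concise Summary gives propofol to everyone first: "Prior to initiation of DHE infusion, the subjects will receive sub-anesthetic doses of propofol infusion". It then says "If propofol infusion is not successful in resolving headache, then the subjects will proceed with DHE infusion per standard of care". The Study termination section states the rule in terms of the pain score: "if patient has less than 50% reduction in pain scores, the study investigators will continue with DHE protocol according to standard of care". For inpatients in whom propofol works, the Concise Summary says "inpatient subjects would resume standard care treatment", without saying whether that includes DHE. The SAP's Study Overview says that failures went on to standard of care and does not name DHE at that point.

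**Follow-up.** Everyone who receives propofol is telephoned at 24 and 48 hours. The items are the current pain score, when the headache returned, and "side-effects from infusion".

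**Analysis.** The SAP compares mean pain at baseline with mean pain at each later time, including 24 and 48 hours, by paired t-test. It describes safety in a Safety Analysis Set that it does not define. Neither analysis has a rule for data collected after DHE or a split by later therapy.

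**The concern.** There are two issues of different weight.

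The first is that the protocol says it will show an advantage over DHE, or over standard care, in speed, durability and tolerability. A single-arm study can estimate what happens after propofol. It cannot say whether that is better than what the same children would have had on DHE. If the comparative wording reaches the report, readers will take a before-and-after result as a comparison of treatments.

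The second bears on results that the SAP does plan. By the time of the calls, some subjects will have had DHE. A fall in pain from baseline to 24 or 48 hours in those subjects reflects propofol, DHE and the natural course of the attack together. A side effect reported on the same call may belong to either drug. Pooling everyone could overstate lasting relief from propofol and misstate its side-effect profile.

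**Working it through.** The documents contain no propofol-versus-DHE calculation to reproduce. The planned 30 subjects come without a power, effect size or reference rate, and nothing here depends on that number.

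**Step 1: can the design address the comparative aims?**

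| Claim | What is measured for propofol | What is measured for DHE |
|---|---|---|
| More rapid relief | Time from start of infusion to first improvement; pain every 10 minutes during infusion and up to one hour after | No pain schedule tied to the start of DHE |
| Sustained relief | Duration from end of propofol to discharge criteria or new therapy; pain at 24 and 48 hours | No duration outcome; 24/48-hour scores exist only in children who had propofol first |
| Fewer side effects | Monitoring, adverse events, follow-up calls | No separate record specified |

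No group receives DHE without prior propofol, and no historical DHE rate is named as a reference in the analysis. The SAP's only tests are against each subject's own baseline.

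**Step 2: whose 24/48-hour data can follow DHE?**

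- Propofol failures, by the protocol's rule. The documents put that rule in two ways: headache not resolved (Concise Summary) and less than 50% reduction (Study termination). These need to be reconciled, because a child who is improved but not pain-free falls on different sides of them.
- Possibly inpatient responders who resume standard care. The Background describes inpatient practice thus: "As an inpatient, our current protocol requires premedication with anti-emetics and DHE dosing every six hours". Several doses could therefore precede a call.

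**Step 3: effect on the nausea rate (illustration).**

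Inputs:
- r = 0.32, nausea with DHE (protocol, Background).
- f = share of subjects who receive DHE. The documents do not give it. The paediatric series cited in the Background reports 80% efficacy and the adult study 95.4%. If DHE went to failures alone, f would be 0.20 or 0.046. I add 0.50 as an assumed upper case.
- Propofol nausea assumed to be zero, to isolate the DHE contribution.

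Formula: points added to the all-subject rate = f × r.

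| f | f × 0.32 | Points added | DHE recipients among 38 |
|---|---|---|---|
| 0.046 | 0.0147 | 1.5 | 1.7 |
| 0.20 | 0.064 | 6.4 | 7.6 |
| 0.50 | 0.16 | 16 | 19 |

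**Step 4: effect on the 24/48-hour pain result.**

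Let d be the extra reduction in pain score that DHE produces among those who receive it. The pooled mean change then contains f × d that is not due to propofol. Each point of d on the 0-10 scale adds 0.20 points to the pooled mean change if f = 0.20, and 0.50 points if f = 0.50. The documents give no value for d in this setting, so the total cannot be stated.

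**The case against.** **No comparison with DHE is planned.** The Study Aim, the primary and secondary outcomes and the SAP's objectives contain none. The comparative language sits in a benefit statement and in a sentence about what the investigators hope. The SAP is dated 2023, after the 2017 protocol version, and does not repeat it. This stands, and it limits the first issue to unsupported wording.

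**The side-effect item most naturally means propofol.** It appears in a follow-up defined for propofol recipients, and the protocol elsewhere uses the bare word for the propofol infusion. The named safety endpoints, cardiopulmonary depression and excessive somnolence, are covered by monitoring and sedation scoring around the infusion. This largely stands: mixing of side effects is possible but not shown. A family on the telephone a day later may still be unable to attribute a symptom, and neither document says how attribution is to be made.

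**The nausea figure may not carry over.** Inpatients receive anti-emetic premedication, and nausea is neither a named endpoint nor on the protocol's list of propofol side effects. This also stands, so Step 3 is an illustration and not an estimate.

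**A stronger reading that the documents do not support.** A reader might infer that the trial contains a propofol-versus-DHE contrast biased towards propofol because DHE is reserved for propofol failures.
- No such contrast is planned.
- The documents do not establish that only failures receive DHE, since inpatient responders return to standard care.
- Any figure for the bias would rest on an assumed response rate and an assumed correlation between a child's responses to the two drugs. With no correlation there would be no such bias.
- Selection of failures would count against DHE, while mixed-in side effects would count against propofol. No net direction can be claimed.

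**Conclusion.** The point holds in two parts. The comparative aims cannot be supported by a single-arm design with no concurrent or specified historical comparator. That is a fault of wording, not a biased test in the SAP. The more consequential part is that the planned 24/48-hour paired t-tests pool subjects treated after propofol with those who were not, and the safety summaries likewise have no split. The pooled change cannot be attributed to propofol alone. Side effects of later DHE may enter propofol's profile, by 6.4 to 16 points for nausea if 20% to 50% of subjects receive DHE. That range rests on the protocol's 32% figure, zero nausea from propofol, and full carry-over of DHE nausea into the follow-up reports. At the adult study's success rate, with only failures given DHE, it would be about 1.5 points. Pain scores during the infusion, before any DHE, are not affected.

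**What to change.** **Wording.** In Introduction and Purpose and in Potential patient benefit, replace the comparative statements with single-arm estimates of propofol response and adverse-event rates, with confidence intervals. State that no comparison with DHE will be drawn. The SAP already describes conduct in the past tense with 38 participants, so the same limit should govern the study report.

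**SAP.**
- Report 24- and 48-hour pain and side effects separately by receipt of DHE or other subsequent therapy, with the number in each group.
- Classify side effects by onset before or after the start of DHE where timing was recorded. Where it was not, the split by receipt is the fallback.
- If the pooled 24/48-hour change is shown, do not attribute it to propofol alone.
- Treat the split as descriptive. Receipt of DHE depends on response to propofol, so the subjects without DHE do not give the propofol effect for all subjects.

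**Cost.** Some rewording and one extra split in the follow-up tables, with no new subjects, visits or treatment changes. The downside is smaller subgroups with wider intervals, and a less favourable claim.
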